34. Principal Investigator's Assurance	22
35. CHECKLIST SECTION.....	24
36. Partial Waiver of Consent for Screening/Recruitment.....	24
37. Partial Waiver of HIPAA Authorization for Screening/Recruitment.....	25
38. Waiver of Documentation of Consent	25
39. Alteration of Consent.....	26
40. Full Waiver of Consent/Parental Permission	27
41. Full Waiver of Consent/Parental Permission (Public Benefit or Service Programs)	28
42. Full Waiver of HIPAA Authorization (Checklist)	28
43. Other Waiver Types (Checklist).....	29

PROTOCOL TITLE: **Improving Healthcare Outcomes in American Indian and Hispanic Transplant Recipients Using Culturally-Tailored Novel Technology (IMPACT)**

44. Vulnerable Populations (Checklist).....	29
45. Medical Devices (Checklist).....	35
46. Export Control (Checklist)	36
47. Data Transfer/Sharing (Checklist)	36
48. Specimen Transfer/Sharing (Checklist).....	37

PROTOCOL TITLE: **Improving Healthcare Outcomes in American Indian and Hispanic Transplant Recipients Using Culturally-Tailored Novel Technology (IMPACT)**

1. Objectives

Aim 1: Examine IMPACT's acceptability and feasibility in AI and HL KT recipients.

1a. We will assess acceptability by patient ratings of satisfaction with the culturally-tailored diet and exercise intervention, as well as the Twistle patient engagement platform.

1b. We will assess feasibility by determining recruitment and retention rates and assessing participant adherence to the IMPACT intervention.

1c. We will determine the ideal personnel hours and number of staff required for the physical therapist/exercise physiologist and registered dietitian nutritionist roles.

Aim 2: Test the efficacy of IMPACT on proximal outcomes (e.g., weight, lipid profile, HbA1c, sleep quality, QOL) and distal outcomes (e.g., occupational functioning) in kidney transplant recipients.

2a. We will assess participants' adherence to the exercise and diet intervention aspects of IMPACT.

2b. We will begin to examine the relationship between adherence to IMPACT and patient outcomes.

2. Background

Kidney transplantation (KT) is the treatment of choice for patients with end-stage kidney disease (ESKD). Although KT reduces cardiovascular events, cardiac death rates in KT recipients remain up to 10 times greater than in the general population.^{1,2} Similarly, KT recipients with diabetes-associated ESKD have higher mortality rates compared to recipients with ESKD due to other causes.^{3,4} New-onset diabetes after transplantation is also a major contributor to the burden of cardiovascular disease.^{5,6} Further, although aggressive treatment with post-transplant immunosuppressive agents^{7,8} has decreased rejection, use of these agents is associated with a host of other complications, such as hyperlipidemia, hypertension, post-transplant diabetes, and glomerulopathy.⁹⁻²² Currently, the most common approach to treating these cardiometabolic complications is medication. However, medications are limited in their effectiveness,^{2,23,24} and patients may face contraindications and unwanted side-effects, given their complex post-transplant immunosuppression regimen.⁹⁻²² Given the tremendous resources that go into evaluating and transplanting ESKD patients, it is important to explore effective, yet less costly, approaches to reducing cardiovascular and diabetes-related risk post-transplant.²

Weight gain in the first year after KT, and especially an increase in fat mass, is a very common contributor to elevated cardiometabolic risk. In addition, low levels of physical activity and reduced physical functioning are common after KT, associated with a reduced quality of life (QOL)²⁵ and poor sleep quality.²⁶ Lifestyle modification (dietary changes and exercise) has been the mainstay for initial management of diabetes and cardiovascular disease for decades in the general population. Because of the presence of both traditional and transplantation-specific risk factors for cardiovascular events and diabetes after transplantation,²⁷⁻²⁹ it is important to validate the feasibility and efficacy of an early post-transplant lifestyle modification specifically for the KT population.³⁰ Although an approach specifically tailored to KT recipients may be an optimal solution,^{31,32} Takahashi's³³ seminal review of physical activity in the KT population noted that previous programs had limited testing (e.g., small sample sizes; brief follow-

PROTOCOL TITLE: **Improving Healthcare Outcomes in American Indian and Hispanic Transplant Recipients Using Culturally-Tailored Novel Technology (IMPACT)**

up),^{17,33-35} and have not resulted in specific lifestyle management guidelines for KT recipients.³⁶ Similarly, a recent Cochrane review of dietary interventions for adults with CKD³⁷ highlighted the limitations of current evidence of dietary interventions on CKD patients. Further, a meta-analysis of multi-behavior lifestyle interventions in chronic disease and community populations³⁸ found that most intervention studies are targeted at White (WH) or African American (AA) patients, with lowest representation of American Indian (AI) or Hispanic/Latina(o) (HL) populations; overall, only 10% of interventions were culturally appropriate to the target population.

In **Improving Healthcare Outcomes in American Indian and Hispanic Transplant Recipients Using Culturally-Tailored Novel Technology (IMPACT)**, we will pilot the feasibility and acceptability of a culturally-tailored, multi-behavior lifestyle intervention using a novel technology for 14-20 AI, HL, and White KT recipients. Because of KT recipients' varied stability immediately post-transplant, and the need to individually monitor their post-transplant immunosuppression regimen,^{1,23,24,33} a critical component of IMPACT will be an individually-tailored exercise and diet plan with a physical therapist/exercise physiologist and a registered dietitian nutritionist, who will work closely with the post-transplant team to carefully monitor patient stability. IMPACT will combine a personalized assessment of the patient's food preferences and access to exercise resources within their environment (based on a standard list of factors developed by our nutrition and rehabilitation experts) along with clinical specifications from the transplant team. Our study is innovative because it addresses previous limitations,^{33,37} while adapting the intervention to meet the needs of the culturally-diverse ESKD population. The final innovation of the IMPACT Pilot is our use of the Twistle Patient Engagement Platform³⁹ to follow-up with participants between their scheduled appointments, ensure adherence to the intervention, collect all questionnaire data, and enhance participant retention.

3. Study Design

Due to heterogeneity among the exercise programs used in previous post-KT studies, it is difficult to make definitive conclusions regarding the benefit of aerobic versus resistance training.³³ **Thus, our project is innovative because it combines instruction that is professionally guided by a therapist, and incorporates a rehabilitation approach to slowly increasing KT recipients' physical activity⁴⁰⁻⁴² until they can engage in exercise at levels consistent with the KDIGO guideline.** We argue that in the current era of personalized medicine, it would not be appropriate to prescribe one form of exercise across all patients. Rather, a tailored approach to physical rehabilitation with the end goal of a patient's ability to meet the KDIGO guidelines (and within their specific cultural environment) is optimal for patient health and outcomes. Our intervention is innovative because it addresses the limitations identified by Takahashi's³³ review of physical activity and the Cochrane review of dietary guidelines³⁷ in the KT population, while having the capacity to be culturally adapted to meet the needs of the diverse ESKD population that exists in the US today.

Another innovation of our approach is to work with the existing resources of the core transplant team in any transplant center (namely, the transplant registered dietitian) and empower that team member to develop a culturally-tailored diet approach

PROTOCOL TITLE: Improving Healthcare Outcomes in American Indian and Hispanic Transplant Recipients Using Culturally-Tailored Novel Technology (IMPACT)

that helps patients reduce weight gain, lower their HbA1c levels, and decrease their risk of post-transplant cardiovascular events. This is an innovative health services research approach that will allow our team to determine the cost effectiveness of expanding the role of the registered dietitian on the KT team in a subsequent R01 project. Only one study of a lifestyle modification intervention targeting diet and exercise with KT recipients has been published, but it lacked a randomized controlled trial because it confounded intervention with health condition and studied patients who were at least 6 months post-transplant.⁴³ In contrast, our intervention will focus on patients when they are still in the hospital immediately post-transplant. Hospitalization has been hypothesized to serve as a "teachable moment" that could more clearly demonstrate to patients the connection between behavior and health and be particularly amenable to making changes in patient health behavior (e.g., in-patients with unhealthy alcohol use, diabetes, pediatrics, cancer).⁴⁴⁻⁴⁷

The most critical innovation of the IMPACT pilot is our collaboration with the makers of Twistle (Fig. 1).³⁹ Twistle is a HIPAA-compliant patient engagement platform designed to perform across all clinical specialties, procedures, and chronic conditions. Twistle is used for patient education, reminders, and secure messaging. Clinicians and patients can automatically send and receive HIPAA-compliant messages including text, emojis, photos, and videos. Twistle has an automation engine that can engage, respond and manage conversations, allowing staff and clinicians to take over conversations that need extra attention. It can also automatically send alerts and follow-up messages based on survey responses and triage appropriately based on pre-defined rules and on-call schedule. Twistle is designed to integrate with electronic health records, registries, databases and predictive analytics tools. It also automatically synchronizes data from smart devices, such as blood pressure cuffs, weight scales, CPAP machines, and

activity trackers. Because Twistle is a multimodal platform, it can deliver messages and reminders through smartphone apps (Apple and Android), text message (SMS), computer browsers, EHR portal and regular landlines using interactive voice response (IVR) or recorded voice. So our intervention

[figure not shown]

Figure 1. Screen shots of Twistle patient engagement platform

with Twistle will be used by those with or without a smartphone, and addresses recent

PROTOCOL TITLE: **Improving Healthcare Outcomes in American Indian and Hispanic Transplant Recipients Using Culturally-Tailored Novel Technology (IMPACT)**

and ongoing concerns regarding broadband internet and provider access in rural communities.^{48,49}

For our research purposes, we will use Twistle to create and deploy our participant questionnaires because it is compatible with RedCap. We will also use it to send personalized reminders and check-in with participants based on the culturally-tailored exercise and diet plan developed by our intervention team to assess and maintain adherence to the intervention. Twistle also enables the data to be pushed to a reimbursement database, so that our research team is triggered to provide participant payments. Finally, we will use Twistle to track participant status throughout the research protocol. The application will allow us to confirm message delivery, patient engagement, and monitor triage alerts.

We will randomly assign participants to either the IMPACT intervention of usual care (UC) prior to their first intervention point. [name] (lead statistician) will develop a random allocation scheme by considering stratification to form blocks with respect to important determinants such as ethnicity, gender, etc. Within each stratum or block, we will accomplish random allocation to IMPACT vs UC with systematic sampling (e.g. alternating the assignment of IMPACT and UC with a random start). This scheme will result in a nearly equal number of patients in IMPACT and UC within a block. We will reduce potential bias using stratified randomization by preventing potentially inferring treatment allocation *a priori*. It also reduces bias by balanced assignment so that potential determinants of outcomes are comparable across intervention groups. We can also use systematic sampling to reduce sampling variation in comparison with simple random sampling. Because of the close interaction between the clinical team and the research interventionists, we will not be able to blind the clinical team to group assignment.^{50,51} After [name] creates the allocation scheme, he will give it to the research coordinator, who will put the allocation assignments into separate sealed envelopes. The research coordinator will place the master list in a locked file cabinet drawer in the office of the PI's Office Administrator. Only the sequence numbers (A1 – block A patient #1, A2, A3, etc.) will appear on the sealed envelopes and the corresponding group assignment will be placed inside the envelope. The research coordinator will open the sealed envelope sequentially and inform the consented participant of his or her assigned group. After random assignment, the research coordinator will direct participants in the IMPACT intervention to the study interventionists (the physical therapist and dietitian).

4. Inclusion and Exclusion Criteria

We plan to recruit participants shortly before or after undergoing KT at the UNM HSC Transplant Center. The Transplant Center provides transplant services to all New Mexico residents as well as the surrounding Pueblos and the Navajo Nation. Reflecting the demographics of the state, only 3% of patients are AA at UNM. Male and female KT recipients aged 18 and older will be eligible for enrollment.

Transplant Patients

Inclusion criteria:

1. Received kidney transplant at the University of New Mexico
2. Greater than 18 years of age

PROTOCOL TITLE: **Improving Healthcare Outcomes in American Indian and Hispanic Transplant Recipients Using Culturally-Tailored Novel Technology (IMPACT)**

3. American Indian (AI) or other race, White (WH) or Hispanic/Latina(o) (HL)
4. Mentally competent

Exclusion criteria:

1. Children under the age of 18
2. Incarcerated patients
3. Pregnant women

Team Members

Inclusion criteria:

1. Transplant clinic staff
2. Key administrators involved in the transplant process

5. Number of Subjects

To estimate the number of patients we can expect to recruit for the study, we used data from the last five years of KT recipients at UNM HSC. The center transplants an average of 33 patients per year. For the study, we plan a 12-month recruitment period. Of all eligible patients who receive a KT, we expect that 80% will agree to participate in our study (n=26), based on previous intervention research with KT patients,^{13,16,17,34,41,52-54} and our own work.⁵⁵⁻⁵⁷ Thus, for this pilot trial, we aim to recruit and retain 14-20 KT recipients. Virtually all of UNM ESKD patients are (a) HL (44%) or AI (33%), (b) income <\$25K, (c) on public insurance, (d) high school or lower education; and/or, (e) low occupational status. Thus, our patient sample will include members of different vulnerable populations that have been underrepresented in past research, and hence prepare us to conduct a formal study in a diverse population.

Team members will include up to fifteen people from the following groups: transplant clinic staff and key administrators.

6. Study Timelines

Participant expected duration in the study will be one year, if they complete all study visits. Patient recruitment and enrollment will be completed in 12 months of the study (Month 4, Year 1 through Month 3, Year 2). Participant follow-up, data analysis, and manuscripts are schedule to be completed in Year 2 of the study.

Project Period: 03/01/2020 – 02/28/2022									
Activity	Year: Month:	01		02					
		1-3	4-6	7-9	10-12	1-3	4-6	7-9	10-12
Project Startup (e.g., hiring and training staff; database creation)		----							
Participant Recruitment		-----		---					

PROTOCOL TITLE: **Improving Healthcare Outcomes in American Indian and Hispanic Transplant Recipients Using Culturally-Tailored Novel Technology (IMPACT)**

Participant Follow-up		
Team Member Surveys		
Data Quality Evaluation and Observation Logging	-----	-----
Data Analysis		-----
Present Initial Findings at Conferences		---
Report and Manuscript Preparation		---

7. Study Endpoints

The primary endpoints for the pilot trial are intervention **acceptability** and **feasibility**. To assess **intervention acceptability** we will measure patients' satisfaction with the interventions with a revised version of the Client Satisfaction Questionnaire,⁵⁸⁻⁶⁰ where higher satisfaction will indicate greater intervention acceptability, and the System Usability Scale (SUS),⁶¹ where higher scores indicate ease of usability. We will assess questionnaire acceptability using open-ended patient questions. In addition to quantifying **feasibility** using **recruitment and retention rates**, to provide concrete estimates of the expected rates of missing data and participant attrition, we will keep a detailed log of relevant factors that could create barriers to subsequent study completion. We will measure time spent sedentary (sitting/lying), standing, and stepping (and the intensity) during awake hours with the activPAL3 accelerometers, and compare these values between the IMPACT and UC groups. Time required for study participation will be measured using survey completion times as well as intervention session time estimates.

In addition to the primary endpoints noted above, we will assess the feasibility and acceptability of collecting a number of patient outcomes that will be the key target outcomes in a large scale R01. A systematic review of 35 randomized controlled trials of exercise training in solid organ transplant recipients, including 9 kidney, 21 heart, 3 lung, and 2 liver transplant studies, found that there were a total of 62 patient outcome measures, including peak VO₂, SF-36 score, and muscle strength.⁵² Of these, our team determined that the most relevant outcomes to assess in our pilot include: (a) variables that we will gather from participants' medical records (i.e., % weight change, lipid profile, and HbA1c); (b) patient reported outcomes, including the PROMIS Sleep Related Impairment⁶² and Sleep Disturbance⁶³ Measures and PROMIS Global Health⁶⁴; and, (c) occupational functioning, using the occupation subscale of the CHART-SF.⁶⁵ The CHART-SF is the most widely used participation measure in rehabilitation research,⁶⁶ and has been used in various ethnic groups.⁶⁷

8. Research Setting

We plan to recruit participants shortly before or after undergoing KT at the UNM HSC Transplant Center. The Transplant Center provides transplant services to all New Mexico residents as well as the surrounding Pueblos and the Navajo Nation. Reflecting

PROTOCOL TITLE: **Improving Healthcare Outcomes in American Indian and Hispanic Transplant Recipients Using Culturally-Tailored Novel Technology (IMPACT)**

the demographics of the state, only 3% of patients are AA at UNM. Thus, their number will be too small to examine as a separate racial group. Male and female KT recipients aged 18 and older will be eligible for enrollment.

9. Resources Available

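### The allocation sequence described, alternation from a random start within strata, is largely predictable, and the coordinator who opens the envelopes also receives the list and fills them

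*Combined protocol and SAP*

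**What the plan says.** The last paragraph of section 3 (Study Design) describes the whole allocation process.

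- **Strata.** The lead statistician builds the scheme "by considering stratification to form blocks with respect to important determinants such as ethnicity, gender, etc". The list of factors is left open.
- **Sequence.** Within each stratum, "we will accomplish random allocation to IMPACT vs UC with systematic sampling (e.g. alternating the assignment of IMPACT and UC with a random start". No random permutation, varying block size or central release is described.
- **Claimed properties.** "We will reduce potential bias using stratified randomization by preventing potentially inferring treatment allocation" before the fact. The systematic method is also defended on efficiency grounds: "We can also use systematic sampling to reduce sampling variation in comparison with simple random sampling".
- **Custody.** Once the statistician has made the scheme, "he will give it to the research coordinator, who will put the allocation assignments into separate sealed envelopes". Then: "The research coordinator will place the master list in a locked file cabinet drawer", which stands in an administrator's office. Envelopes show only a stratum letter and a patient number. At enrolment: "The research coordinator will open the sealed envelope sequentially and inform the consented participant of his or her assigned group".
- **Blinding.** "we will not be able to blind the clinical team to group assignment".

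**The concern.** Two separate weaknesses sit in one paragraph.

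First, the stated benefit and the stated method conflict. Stratification balances known factors between arms; it does not hide the next assignment. Under alternation only the first patient in each stratum is randomized. Anyone who knows the rule and the last assignment in that stratum knows the next one. Past assignments are visible because the clinical team is not blinded, and the envelope label shows stratum and position.

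Second, whatever the sequence, the role that opens the envelopes has already handled the complete list.

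If someone with foreknowledge influenced who was approached, or when, the IMPACT versus usual care comparisons would be biased. These are the Aim 2 efficacy outcomes (section 1), the activPAL comparison (section 7) and the diet and exercise comparisons (section 13). The effect-size and go/no-go inputs for the later trial (section 13) would carry the same bias. Steering particular patients into or away from IMPACT could also shift satisfaction, adherence and retention in that arm, which feed the primary endpoints.

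**Working it through.** The plan gives no figure for predictability, so there is nothing to reproduce. It was calculated directly.

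**Inputs.** N = 14 to 20 patients (section 5). About 1:1 allocation within strata (section 3). The number of occupied strata, k, is not stated. It is assumed to run from 1 to 6, where 6 would be three ethnic groups by two genders, with strata of near-equal size.

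**Step 1. Alternation, guesser who knows the rule and the past assignments.** One assignment per stratum is random and the rest follow.

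- Share fully determined = (N − k)/N
- Expected share guessed correctly = (N − k/2)/N, because the first in each stratum is a coin toss
- Number of possible lists = 2^k

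| N | k | Determined | Guessed correctly | Possible lists |
|---|---|---|---|---|
| 14 | 1 | 13/14 = 92.9% | 13.5/14 = 96.4% | 2 |
| 14 | 3 | 11/14 = 78.6% | 12.5/14 = 89.3% | 8 |
| 14 | 6 | 8/14 = 57.1% | 11/14 = 78.6% | 64 |
| 20 | 1 | 19/20 = 95.0% | 19.5/20 = 97.5% | 2 |
| 20 | 3 | 17/20 = 85.0% | 18.5/20 = 92.5% | 8 |
| 20 | 6 | 14/20 = 70.0% | 17/20 = 85.0% | 64 |

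Equal strata do not drive this. A simulation with ethnicity strata of 44%, 33% and 23% (the first two from section 5, the third assumed to be one group) gave 89.4% correct at N = 14 and 92.5% at N = 20.

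**Step 2. Alternation, guesser who does not know the rule.** This person picks whichever arm is behind in the stratum and tosses a coin on a tie. Odd positions are ties (0.5 correct) and even positions are certain. For N = 14, k = 3 (strata of 5, 5 and 4) there are 8 odd and 6 even positions: (8 × 0.5 + 6)/14 = 71.4%. Over k = 1, 3, 6 the results are 75.0%, 71.4%, 71.4% at N = 14 and 75.0%, 72.5%, 70.0% at N = 20.

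**Step 3. Comparator: permuted blocks of randomly varying size.** The guesser is the best possible one, who knows the menu of block sizes and the full history. Rates come from exact enumeration of all histories, and simulation of 20,000 lists with the arm-behind strategy agreed within 0.001.

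| Block sizes | N = 14, k = 1 / 3 / 6 | N = 20, k = 1 / 3 / 6 |
|---|---|---|
| 2 and 4 | 71.7% / 68.5% / 65.5% | 71.9% / 69.4% / 66.7% |
| 4 and 6 | 68.1% / 64.6% / 57.6% | 68.5% / 66.2% / 61.5% |

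Pure chance is 50%.

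**Step 4. Reading the figures.** With three strata, a guesser who knows the rule is right 89-93% of the time under alternation, against 65-69% under blocks. A guesser who does not know it reaches 71-73% under alternation. Most of the gap therefore comes from knowing the rule, and the protocol prints that rule as its example.

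**Step 5. Custody.** A coordinator who has read the list knows 100% of assignments under any sequence, so changing the sequence alone does not close that route.

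**The case against.** - **Alternation is offered only as an example.** True: another form of systematic sampling is not excluded, and the final rule and strata are left to the statistician. But no other method is described, the paragraph goes on to defend systematic sampling, and a list made by strict alternation would comply with the text. The 79-98% range is conditional: it needs alternation to be adopted, and someone who knows the rule and tracks assignments by stratum.
- **The route from prediction to bias is not shown.** This stands. The text available for this review does not say who approaches or consents patients; section 20 uses the passive voice, and part of section 9 was not available. The unblinded clinical team matters only if it influences entry. Using one job title for all envelope steps most naturally means one person, but the protocol does not say so.
- **There is little room to reorder patients.** Entry largely follows transplant date, and 14-20 patients over 12 months is about 1.2-1.7 a month (14/12 and 20/12). This lowers the risk. Selective approach or persuasion remains possible.
- **Safeguards exist.** Envelopes are sealed, opening follows consent and the list is locked away. None of these helps when the next assignment follows from the last, or when the opener also filled the envelopes.
- **Analysis could adjust.** Baseline activPAL and listed covariates would allow partial adjustment for measured imbalance, with few patients. Unmeasured selection could not be repaired.
- **It is a pilot.** Acceptability and feasibility are not mainly between-arm contrasts, and section 13 does not expect significant differences. This limits the weight. It does not resolve the contradiction.

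**Conclusion.** The concern holds. The paragraph claims protection against prediction that its only described method does not give, and it lets the role that opens the envelopes hold the list first. The size is that of Step 1 if alternation is used, and it rests on the assumed 1 to 6 near-equal strata. The custody weakness needs no such assumption about strata or sequence. Actual selection is a risk and not a demonstrated fact. The point should be fixed, but it does not threaten the pilot's main feasibility purpose; what it puts in doubt is the between-arm information carried into the larger trial.

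**What to change.** Two changes are essential.

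1. Replace systematic or alternating assignment with a computer-generated sequence of permuted blocks of randomly varying size, not disclosed to study staff, within a small set of strata fixed in the protocol. Block sizes (for example 2 and 4, or 4 and 6) and factors are the statistician's choice.
2. Have the statistician, or someone outside enrolment and intervention, hold the list and prepare opaque, sequentially numbered envelopes, or release assignments electronically one at a time after consent. The coordinator should neither see the list nor fill envelopes.

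Also delete the sentence crediting stratification with preventing inference and the systematic-sampling rationale, and state who approaches and consents patients if the protocol does not already do so.

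**Cost.** One rewritten paragraph, any ethics review that the amendment needs, and a short task for the existing statistician. If enrolment has begun, the change of sequence should be dated and documented. Separating custody costs no balance. The new sequence costs some, shown here as the chance that the arms differ by 4 or more patients (exact calculation for the 3 and 6 near-equal strata):

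| Strata | N | Alternation | Blocks 2/4 | Blocks 4/6 |
|---|---|---|---|---|
| 3, near-equal | 14 | 0% | 2.1% | 5.0% |
| 3, near-equal | 20 | 0% | 3.1% | 6.8% |
| 3, at 44/33/23% | 14 | 0% | 2.6% | 7.5% |
| 3, at 44/33/23% | 20 | 0% | 2.5% | 7.2% |
| 6, near-equal | 14 | 0% | 14.7% | 30.1% |
| 6, near-equal | 20 | 12.5% | 15.6% | 25.3% |

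With six strata the loss is real, above all with blocks of 4 and 6. Few strata and the smaller blocks keep it to about 2-3%.
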